tolerate well the dose of varenicline or placebo 1.0 mg per day in single or divided doses will be discontinued from the study.

Due to a shortage of varenicline in the US, the study medication in the **Pilot** study was provided by Apotex, Canada, apo-varenicline, which was on a temporary importation allowance from the FDA. US-made generic varenicline was FDA approved in August of 2021, made available for purchase in November 2021, and is currently used for the **main** study protocol.

Medication Distribution: Study staff will distribute or send via priority mail varenicline or identically appearing placebo with instructions on how to take the study medication on the following schedule:

Baseline/Week 0: a 2-week supply Week 2: a 2-week supply Weeks 4 & 8: a 4-week supply

In the case of having participants who are traveling or experience unforeseen circumstances, we will coordinate with the research pharmacy to adapt the current distribution schedule to the participant's needs to ensure they receive enough study medication.

Medication adherence: As part of the virtual weekly visit, participants will be asked to show their used and unused study medication each week to complete a weekly medication count to assess compliance. Missed doses will be discussed to try to ascertain the reason(s). Reasons for missed doses and/or patterns of missed doses will be incorporated into the vaping cessation sessions and every effort will be made to ensure proper subject dosing. Text messaging will encourage participants to take study medications as instructed. Participants will be instructed to bring all empty and unused study medication to in-person study visits. Unused medication will be cataloged by site staff to verify data reported by the subjects.

The emocha smartphone app will be used during the treatment period to remind participants via text message to take their study medication, document medication adherence and medication identification, and record daily assessments. emocha will also be used for appointment reminders. When emocha is not available, participants will use REDCap to upload a time-stamped photo to confirm use of study meds. Recorded dosing will be incentivized with micropayments. emocha and REDCap have embedded privacy protections.

Daily surveys are estimated to take 1-5 minutes each. To maximize compliance, we will adhere to best practice guidelines including training on the software at baseline and as needed throughout the study, ongoing compliance monitoring and follow-up with participants who demonstrate low adherence. Micropayments will be made to incentivize each survey completed (\$1 per emocha video and survey completion, up to \$2 daily).

c. Devices to be used: N/A

d. Interventions (for participant randomized to varenicline or placebo arms)

- i. **QuitVaping** behavioral support sessions will be delivered weekly during the 12-week treatment phase via videoconference or in-person. QuitVaping is a manualized intervention based on the American Lung Association smoking cessation program⁴⁷ modified with teen friendly content and language for adolescent vaping cessation from the vaping section of teen.smokefree.gov³² and the Truth Initiative, including:
 - How to quit vaping: includes setting a quit date and standard quit date preparation modified for teen vaping;
 - Your first day without vaping;
 - Dealing with vape cravings, with standard behavioral methods for nicotine cravings and a prompt to call [name] or [name], or chat with an expert online using the National Cancer Institute's LiveHelp service;
 - Understanding your vaping triggers;
 - Vaping addiction and nicotine withdrawal;
 - Anxiety, stress, depression and vaping;
 - How does vaping affect the environment? Your health?;
 - Your likelihood of using other drugs or smoking;
 - How to say no to vaping with friends;
 - Information on the corporate exploitation of youth through the marketing of addictive products for profit, corporate support for vaping memes and corporate funding of social media influencers to promote vaping.

Before behavioral intervention sessions, participants will fill out assessments of vaping craving and collect saliva for cotinine testing (the latter only occurring if the participant self-reports nicotine abstinence since the last weekly visit). To refine and tailor these interventions to be maximally appealing to and effective for adolescents who vape, we will ask participants for weekly feedback on the appeal, relevance, and effectiveness of the educational topics and skills covered in the program. For participants randomized to the EUC arm, weekly sessions will only consist of non-directive support and assessments noted in the Time and Events Table, including saliva samples for cotinine (collected only to bio-verify self-reported nicotine abstinence).

| Time | Activities |
|--------|---|
| 5 mins | Check-in on adverse events, vaping exposure, and medication adherence |
| 3 mins | New educational content |
| 7 mins | Review of education material and skill/behavior goal |

CBT Structure

Prior to initiating the study intervention, interventionists will complete training conducted by [name] or other doctoral members of study staff on QuitVaping sessions. This will include didactic training on vaping and vaping cessation in adolescents, study methods, theoretical rationale, and background information on the behavioral and pharmacologic interventions. At the end of the training, leaders must achieve a minimum score of 80% on the fidelity scale based on their facilitation of two simulated sessions before they lead a session.

e. Enhanced Usual Care (EUC)

i. TIQ (This is Quitting) is a free, publicly available text message vaping cessation program from Truth Initiative, designed specifically to help adolescents who vape nicotine quit. The program is grounded in theory-driven and empirically validated tobacco cessation treatment strategies for young people,⁴⁸ national cessation treatment guidelines,⁴⁹ the Mayo Clinic 5-E Model of Wellness Coaching,⁵⁰ and the Truth Initiative qualitative research and social media observations of young e-cigarette users.⁵¹ TIQ is reported to have been used by over 70,000 youth in the first year after its launch in 2019.⁵² TIQ texts messages with young people who have attempted to, or successfully, quit e-cigarettes, together with evidence-based tips and strategies to quit and stay quit. The language in TIQ is tailored based on the age and products used by the participant to give adolescents appropriate recommendations about quitting.

Participants who set a quit date receive messages for a week preceding it and 30 days afterward that include encouragement and support, skill- and self-efficacy building exercises, coping strategies, and information about the risks of vaping, benefits of quitting and cutting down to quit. Keywords "CRAVE," "STRESS," or "SLIP" provide on-demand support. Users can unsubscribe anytime by texting "STOP." The teen version of the program (ages 13–17) refers to e-cigarettes as JUUL/JUULing, whereas the young adult version (YA, ages 18–24) uses several terms (e.g., vaping, e-cigarette).⁵²

Participants in all three arms will be introduced to TIQ in the first session (week 0) and encouraged to sign up. Use of digital resources will be discussed and tracked in subsequent sessions along with troubleshooting of any problems. Any participant who does not have a compatible phone or for whom the texting program would pose a financial burden will be given a phone to use for the study.

f. Data to be collected

Questions derived from the PhenX Toolkit⁵³ will be collected during the phone screen to assess for demographics as well as other enrollment criteria, such as vaping and smoking history.

Demographics will be re-assessed by self-report during the enrollment visit.

Medical History will be assessed during the enrollment visit.

Population Assessment of Tobacco and Health (PATH) Study Data Collection Instruments⁵⁴

The following questionnaires from PATH will be administered at the enrollment visit: Age of initiation, lifetime quantity and frequency of tobacco use, prior cessation attempts for vaped nicotine, other substance vaping, use of other forms of tobacco, cannabis products, alcohol, non-medical opioids, and other addictive substances.

Willingness to Quit (WTQ) vaping in the next 30 days will be queried at the phone screen and enrollment visit with the PATH questionnaire on serious thoughts about quitting all tobacco products.

Motivation to Quit (MTQ)⁵⁵ (PhenX ID=710501) is a single item measuring motivation to quit vaping among those who want to quit vaping. It will be administered at enrollment with the PATH questionnaire.

The Columbia-Suicide Severity Rating Scale Screener (C-SSRS)⁵⁶ will be used to assess suicidal ideation in the past six months.. This screener will be administered at enrollment and will help determine current suicidality incompatible with safe participation in the study.

Flavor Preference⁵⁷ Youth who vape are far more likely than adults to report using fruit, mint, and candy flavored vapes (OR=21(95% CI: 6, 75)).⁵⁸ This 5-item youth questionnaire will be used at enrollment to query e-cigarette flavor use and preference.

The Peer and Family Influence on Smoking⁵⁹ (PhenX ID=710901) will assess at enrollment smoked and vaped tobacco use by those in the participant's household, dormitory, suite or apartment, and perception of use by their immediate social networks. This 5-item measure can be self- or interviewer-administered. It is validated for ages 12-22, and its use up to age 26 has been recommended as has application of the questions to other tobacco use (e-cigarette and hookah).

The E-Cigarette Dependence (ECDI)⁶⁰ will be administered at enrollment, baseline, week 12, and week 24 to assess the severity of nicotine dependence, which has been reported to correlate significantly with cotinine as a biomarker of nicotine exposure. ECDI scores of \geq 4, corresponding to at least mild nicotine dependence will be required for enrollment. The ECDI has been shown to be valid and reliable among e-cigarette users and dual users of e-cigarettes and combusted tobacco.

The Alcohol Use Disorders Identification Test (AUDIT)^{61,62} was developed by the World Health Organization (WHO) as a simple screening tool to identify hazardous or harmful alcohol use. The AUDIT will be administered at the enrollment visit and at end of the treatment and follow-up phases of the study to detect change from baseline in harmful alcohol use.

The Cannabis Use Disorders Identification Test (CUDIT)⁶³ will be administered at the enrollment visit and at end of the treatment and follow-up phases of the study to detect change from baseline in symptoms of cannabis use disorder.

The Questionnaire of Vaping Craving (QVC)⁶⁴ is a brief, 10-item, valid and reliable measure of vaping craving that queries desire and intent to vape and anticipation of positive outcomes related to e-cigarette use that will be administered at enrollment, baseline, and weekly via REDCap.

Minnesota Nicotine Withdrawal Scale (MNWS)⁶⁵ is a valid, reliable, 9-item self-rated scale of urge to smoke (craving); depressed mood; irritability, frustration or anger; anxiety; difficulty concentrating; restlessness; increased appetite; difficulty going to sleep; difficulty staying asleep,

on an ordinal scale from 0 (not at all) to 4 (extreme). It will be administered at enrollment, baseline, and weekly via REDCap.

The Concise Health Risk Tracking Instrument (CHRT-SR)^{66,67} will be administered to provide a sensitive assessment for change in suicidality to supplement open-ended adverse events queries at each study visit during the treatment phase. The CHRT-SR is a reliable and valid measure for examining severity of suicidal thoughts and associated risk factors and is sensitive to change in adolescents. It will be administered at baseline and each monthly assessment visit during the treatment and follow-up phases. Clinically trained study staff will follow-up on any positive responses.

The Mood and Anxiety Symptoms Questionnaire (MASQ-D30)⁶⁸ is a 30-item adaptation of the 96 item MASQ that is a quick, valid, and reliable assessment of depression and anxiety in adolescents that will be administered at enrollment, baseline, and each assessment visit.

Neuropsychiatric Adverse Events Interview (NAEI)³⁶ is a semi-structured interview designed to systematically assess the presence and severity of specific neuropsychiatric symptoms and will be administered at enrollment, baseline and at each assessment visits. This instrument will be asked in regards to the past six months (at enrollment) and since the last assessment visit (all other timepoints).

Adverse Events will be assessed weekly by the study staff via REDCap during the treatment phase and then monthly during assessment visits to assess the tolerability of the study procedures.

Concomitant Medications will be assessed by self-report at each visit.

Peer Network Stability: At baseline, V12, and 3-month follow-up, participants will be asked to list and rank up to 10 friends in order of closeness, using a modified version of the "concentric circles of closeness" sociometric measure used in. ^{80, 82} Participants will generate their friends' names by free recall to ensure (1) friends included in the study could come from any context and (2) participants designated only individuals whom they truly considered to be friends.⁸¹ A friendship network instability index will be created by calculating the absolute value of the sum of each peer's rank change divided by the total number of peers the adolescent listed at the consecutive time points to account for differences in network sizes.⁷⁹

Modified Mental Health Youth Satisfaction Survey(YSS)⁶⁹ is a 26-item self-rated survey of youth perception of services in 5 domains: access to services; appropriateness of services; cultural sensitivity; participation; and treatment outcome whose internal consistency ranges from 0.70 - 0.94. It has been widely used in state mental health systems to assess youth satisfaction with services and will be given at week 12 to assess participant satisfaction with the intervention.

The Impulsive Behavior Scale (UPPS-P) – Short⁷⁰ will be given at enrollment to assess five components of impulsivity, including sensation seeking, lack of premeditation, lack of perseverance, negative urgency, and positive urgency. Scores on many of these factors have been shown to relate to risk behavior.

The Wechsler Test of Adult Reading (WTAR)⁷¹ will be used to assess speech and dictation and derive an estimated IQ at enrollment.

The Behavior Rating Inventory of Executive Function—**Self-Report (BRIEF-SR)**⁷² is a standardized 80-item self-report behavior rating scale that assesses impulsivity in cognition, behavior, and executive functioning skills. The BRIEF-SR will be administered at enrollment and week 12.

emocha Mobile Health is a mobile health platform that uses video technology and human engagement to monitor patient behavior and enable remote engagement in clinical trials. The emocha platform is globally compliant in terms of data protection standards, including GDPR ready, EU-US Privacy Shield certified, and HIPAA compliant. For those randomized to varenicline or placebo, emocha will be used to send twice daily reminders to take study medication and remotely monitor study medication dosing. Participants will record daily vaping either via emocha or REDCap.

Measures of Vaping abstinence: Saliva will be collected weekly during the treatment phase and then monthly for semi-quantitative cotinine measurement to verify nicotine abstinence in participants who self-report abstinence. Only at enrollment and baseline will cotinine be collected despite self-report to verify use. For in-person sessions, saliva will be collected before the session. For remote sessions, a handout with instructions, materials, and barcoded kits unique to participant will be mailed to participants to perform weekly before their weekly assessment visits. We developed SOPs for safe at home collection and mailing of biological specimens, a procedure we piloted during the closure of MGH clinical research facilities from March-June 2020. Semi-quantitative cotinine of <30ng/ml will validate self-reported nicotine vaping abstinence since the last visit. Those who report no vaping use since the last study visit but who have a cotinine >30ng/ml will be considered non-abstinent at that visit for the analyses.

Measures of smoking abstinence: Carbon monoxide (CO) in expired air will be measured at enrollment with a small, hand-held CO monitor. To do so, participants will blow into a straw attached to the device, a Bedfont Smokerlyzer II (Kent, England), following a 15-second breathhold to verify self-report of non-smoking status. Expired CO <5 parts per million (ppm) is consistent with smoking abstinence. Assays for NNAL will be conducted on urine collected at baseline and weeks 12 and 24. NNAL <10pg/ml will be considered a more sensitive verification of self-report of no combusted tobacco use in the past 2-3 months. Participants with an NNAL of <10pg/ml at baseline and >10pg/ml during the study will be considered to have initiated combusted tobacco use during the trial.

Timeline Follow-Back (TLFB): The TLFB will assess tobacco vaping, smoking, cannabis, and alcohol use. It will be administered at enrollment, baseline, monthly, and follow-up visits. A modified TLFB of vaping in the past 7 days will be administered at weekly intervention visits.

**Pregnancy test:** Urine will be collected from biological females at enrollment, baseline, week 4, week 8, and week 12 for a pregnancy test.

Drug testing: Urine will be collected at enrollment, baseline, and monthly assessments to screen for recent use of cannabis, amphetamines, methamphetamine, cocaine, opiates, barbiturates, benzodiazepines, phencyclidine, methadone, and oxycodone. Quantitative assessment of THC metabolites in urine will be conducted at baseline, week 12, and week 24 to assess for new cannabis use or change in cannabis use during the trial.

Perceived treatment assignment: To assess participants' guess of their treatment assignment, participants will be asked, "what treatment do you think you received? This will be followed by one open-ended question: "Why do you think you received that treatment?" No clarifications will be asked, nor will participants be probed to expand on their answers. This question will be asked either at the end of the week 12 visit or their termination visit.

DNA Collection (saliva) and Analysis: DNA samples will be collected at enrollment using Oragene (OGR-500) saliva kits. Participants may be asked to provide a second sample if a recollect is recommended after DNA extraction (i.e., there is very little DNA in the sample). Participants are not required to provide another sample if they do not wish to do so. Once extracted, samples will be transferred to long term storage until genotyping. Samples will be stored with a unique participant ID.

GWAS Genotyping: The Broad Institute will perform genotyping (array-based) of subject samples and subsequent in-depth analysis of the data, which will allow us to detect alterations in the genome including point mutations, small insertions and deletions, chromosomal copy number alterations and translocations. These experiments are intended to help identify candidate genes involved in the physiopathology of neurological and psychological diseases. The molecular information generated from these samples will not be returned to subjects at any time.

Data from this study may result in communications in journals or at scientific meetings. Subjects will not be identified in those communications. To facilitate research, the genetic information generated may upon publication be deposited in protected databases (such as dbGAP) available only to bona fide researchers with specific scientific questions who promise to try not to identify individuals. The data will be sent to these banks in a coded manner and again will not contain any traditionally used identifiers such as name, address, phone number, or social security number. Although we cannot predict how genetic information will be used in the future, there are many safeguards in place, and we do not think that there will be further risks to patients' privacy and confidentiality by sharing such information with these banks.

The Broad Institute will not be involved in subject ascertainment. Prior to the transfer of biospecimen aliquots to the Broad Institute, samples will be re-encoded at the collaborator's institutions. No identifying patient information will be shared with Broad scientists at any time. Some limited clinical data will be obtained from collaborators and only de-identified clinical data will be shared with the Broad Institute.

Genetic Data Protection: In addition, steps will be taken to protect the confidentiality of genetic data as outlined:

1) All MGH study staff are trained to make confidentiality the first priority.

- 2) No genetic research data will be entered into the medical record.
- 3) The results of the genetic analyses will not be shared with participants, their family member(s), or unauthorized third parties.
- 4) Genetic data are encoded using coded identifiers. These codes, rather than personal identifiers, are used in any analytic datasets. The code key linking coded identifiers to personal identifiers is kept in an access-restricted, password-protected electronic file and is not shared with the genetic laboratories.
- 5) Consent forms are stored in locked cabinets apart from demographic and diagnostic data.
- 6) Samples and genetic data stored in the laboratory will be identified only by the code numbers and laboratory personnel will not have access to personal identifiers.
- 7) The most risk would be identification of individuals in the publicly shared database. To prevent this, computerized data files provided to other investigators will not include any of the HIPPA-defined personal identifiers. Published material will not identify subjects.

COVID-19 Design Consideration

This protocol includes data collection and interventions that can be completed either inperson or virtually. These visits and assessments can be safely conducted in-person with ample precautions in place, and standard operating procedures to ensure the safety of the participants and staff have been written, reviewed, approved by our institution's COVID-19 safety officers, and are in place for our ongoing research protocols. Remote intervention and assessment visits may be required due to COVID-19 safety concerns, and we have piloted procedures for shipping study medication and specimen collection kits to participants' homes.

Early Termination and Relapse

Participants will be encouraged to attend all study visits, regardless of vaping status or ongoing use of study medication. Participants may voluntarily discontinue study procedures at any time for any reason. Participants may be discontinued if their continued participation in the study presents an undue risk to their health as determined by the principal investigator or if they are unable or unwilling to follow study procedures. For any participant who discontinues treatment for any reason, an early termination visit will be conducted to assess vaping outcomes, nicotine craving and withdrawal, clinical symptoms, and adverse effects. Every effort will be made to contact participants who do not return for a scheduled visit. In any circumstance, every effort should be made to document subject outcome. Study staff will inquire about the reason for withdrawal, request the participant to return all unused investigational product(s), request the participant to return for a final visit, if applicable, and follow-up with the participant regarding any unresolved adverse events. Three telephone calls and one letter will be sent to participants who are lost to follow-up to schedule the early termination visit.

Participants will be terminated from the protocol if the research team determines that their continued participation is unsafe or not in their best interest (e.g., in circumstances where there is deterioration in their mental or physical health judged to require a change in medication or hospitalization). If a participant is discontinued, we will refer them to clinical resources for follow-up care or consultation, and we will ask them if this information that can be disclosed to their parents/guardians as applicable to help coordinate and facilitate care.

Study Compensation

Participants will be compensated \$30 for the enrollment visit and all subsequent weekly and follow-up visits. Participants will be paid \$50 (varenicline and placebo) or \$100 (Enhanced Usual Care) for completion of monthly visits during the treatment period. Participants will be paid up to \$2 per day (up to \$168 total) for emocha medication adherence and REDCap survey completions (for those not randomized to EUC). All participants who complete the study will be automatically entered into a raffle for a study completion bonus. For a more detailed description of our payment schedule, refer to the table below. Participants will be reimbursed up to \$15 for necessary travel related to in-person visits. Participants will be compensated for study visits either via MGB-issued check or using the MGB Advarra Participant Payment system, a cloudbased application that provides subjects with a reloadable Visa card that is credited with fixed stipends following specified data collection points. Participants will be informed of Advarra policy during the consent process. After agreeing to participate in the study, participants will also be asked to sign a "Advarra Participant Payment Card Acknowledgement of Receipt" form to certify their understanding of Advarra Participant Payment policies. The form will require participants to print and sign their name and provide their social security number. If the participant is under 18 years old, then parent/guardian information including date of birth, social security number, and address will be collected. Advarra acknowledgment forms will be stored in a locked study cabinet. Travel reimbursement as well as emocha/REDCap adherence will issued to participants as a lump sum via check at the conclusion of their study participation. Participants will be paid using gift cards if they cannot be paid via Advarra/check using a social security number/individual taxpayer identification number.

| Visit/Week | Varenicline/Placebo | EUC | | |
|------------------|---------------------|------|--|--|
| Enrollment | 30 | 30 | | |
| Weeks 0, 1, 2, 3 | 30 | 30 | | |
| Week 4 | 50 | 100 | | |
| Weeks 5, 6, 7 | 30 | 30 | | |
| Week 8 | 50 | 100 | | |
| Weeks 9, 10, 11 | 30 | 30 | | |
| Week 12 | 50 | 100 | | |
| Week 16, 20, 24 | 30 | 30 | | |
| Emocha + surveys | 168 | 0 | | |
| Total | 738 | 720 | | |
| Raffle Bonus | 450 | 468 | | |
| Grand Total | 1188 | 1188 | | |

Payment Schedule

VI. BIOSTATISTICAL ANALYSIS

Statistical Design and Power:

Response estimates are based on 2 studies of the effect of varenicline or placebo plus brief weekly individual behavioral treatment for smoking cessation in adolescent smokers with nicotine dependence of a similar age range. One reported modest medication adherence (63% took 100% of dispensed doses) and high dropout rate (45%) which may underlie low abstinence

rates (<10%) in both groups. We speculate that this trial under-estimates the therapeutic effect of varenicline for adolescent smoking cessation with more optimal treatment adherence. Additionally, potentially important participant characteristics, such as the proportion living with smokers, was not reported and may significantly impact abstinence outcomes in adolescents. In this trial, we will assess smoking and vaping in members of the household (or dorm) and in the primary peer group, and daily text message reminders to take medication and remotely observed dosing via emocha or REDCap will encourage medication adherence.

Continuous abstinence rates for weeks 9-12 of a 12-week intervention in the Pfizer report to the FDA in the varenicline arm ranged from 10-35%. Lowest abstinence rates (10%) were in older adolescents (ages 17-19) assigned to low dose varenicline (0.5 mg bid). In the proposed trial, adolescents who weigh >55kg, more likely amongst older adolescents, will be assigned to 1.0 mg bid as tolerated. Younger adolescents had numerically higher abstinence rates on 0.5 mg bid than 1.0 mg bid, regardless of weight, 16-21% versus 35%. This may have been due to tolerability issues. While there were no differences between any treatment arm in neuropsychiatric adverse events, the high dose group reported numerically more nausea, vomiting, and headache than the low dose and placebo groups. Those aged 17-19 with weight >55kg had better abstinence rates with 1.0 mg bid. Thus, we propose to dose by weight, not age, to employ flexible dosing as follows: All participants will be assessed for tolerability of 0.5 mg bid at the end of study week 1. Participants who weigh >55 kg who tolerate 0.5 bid with no complaints will be offered an increased dose of 1mg bid. Other participants will be continued at 0.5 mg bid.

The primary aim of this trial is to detect whether varenicline added to behavioral treatment significantly increases vaping abstinence rates compared with behavioral treatment alone. We have computed power over a range of outcomes. It is likely that varenicline will need to have a significant effect, such as doubling abstinence rates, to be considered appropriate for youth treatment. Such a significant increase in abstinence with varenicline over that achievable with low cost behavioral and digital intervention is clinically important because it would be warranted to justify the risk and expense of starting medications in this adolescent population.

Data Analysis:

Missing data:

Missing or incomplete outcome data from study week 9 to 12 will be imputed 40 times using multiple imputation via chained equations (MICE).⁷³ Outcome data will be imputed using three predictors collected at the baseline visit: biological sex (male versus female), environment (secondary school versus post-secondary school), and severity of nicotine dependence (the Penn State Electronic Cigarette Dependence Index, a summed score ranging from 0 - 20).⁷⁴ Imputation will be done via fully conditional specification with predictive mean matching using linear models for continuous data and logistic regression for binary variables.

Analyses of safety and efficacy will be conducted separately for participants assigned to Canadian manufactured, apo-varenicline or placebo (pilot) and for participants assigned to US generic Par Pharmaceutical manufactured varenicline (main trial). Analyses on the combined samples of Apo-varenicline and Par pharmaceuticals varenicline will be conducted if appropriate. If combined analyses are considered to be appropriate, these will be considered in the primary analyses.

Statistical method:

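### The friendship instability index takes the absolute value after summing, so any re-ordering of the same friends scores zero, the same as no change (minor; one sentence to correct)

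*Combined protocol and SAP*

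**What the plan says.** The rule is in the Peer Network Stability entry of section V.f, Data to be collected. "At baseline, V12, and 3-month follow-up", "participants will be asked to list and rank up to 10 friends in order of closeness", with names given by free recall. The scoring sentence reads "A friendship network instability index will be created" by "calculating the absolute value of the sum of each peer's rank change", and this is "divided by the total number of peers the adolescent listed at the consecutive time points to account for differences in network sizes". The entry cites reference 79, an unpublished thesis, as its source. It gives no equation and no worked example.

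The Time and Events table schedules the measure at baseline, week 12 and week 24, in the block for descriptions, effect modifiers and covariates. The formula is not restated anywhere else. Section VI, Biostatistical Analysis, does not mention the index.

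**The concern.** An instability index should be lowest when the network has not changed and should rise as it changes. This one sums signed rank changes and takes the absolute value of the total. A friend who moves up pushes others down, so the signed changes offset each other.

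A programmer who followed the sentence literally would get a variable that cannot see changes in closeness order among the same friends. If it were later used as a descriptor or effect modifier, a flat result could come from the scoring alone. The sentence also leaves open what the denominator counts and what rank to give a friend who is on only one of the two lists. If these are settled after the data are seen, that is analytic freedom the plan could easily remove.

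**Working it through.** The documents give no numerical value for the index, so there is no figure to reproduce. The check is algebraic.

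**Inputs, all from the Peer Network Stability entry.** Ranks run 1 to n, with n at most 10. The numerator is |Σ(r₂ − r₁)|, where r₁ and r₂ are a peer's ranks at two consecutive time points. The denominator is the number of peers listed, which could mean one list (n), both lists (2n) or distinct peers.

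**Same friends, no ties.** Both sets of ranks are 1 to n, so

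Σ(r₂ − r₁) = n(n+1)/2 − n(n+1)/2 = 0, and the index is |0|/n = 0.

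This holds for every order. Enumerating all orders for n = 2 to 8 (40,320 of them at n = 8), and drawing 200,000 random orders at n = 10, gave 0 each time.

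**Full reversal of 10 friends.** The changes are +9, +7, +5, +3, +1, −1, −3, −5, −7, −9.

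- As written: |0|/10 = 0.
- Absolute value per peer: 2 × (9+7+5+3+1) = 50, so 50/10 = 5.0, or 50/20 = 2.5 if both lists are counted.

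**Random re-ordering, absolute value per peer.** The mean of Σ|r₂ − r₁|/n is (n² − 1)/(3n).

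| n | Index as written | Mean, per-peer absolute values | Full reversal, per-peer absolute values |
|---|---|---|---|
| 4 | 0 | 15/12 = 1.25 | 8/4 = 2.0 |
| 6 | 0 | 35/18 = 1.94 | 18/6 = 3.0 |
| 10 | 0 | 99/30 = 3.3 | 50/10 = 5.0 |

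The table divides by one list. Counting both lists halves the last two columns; at n = 10 the mean becomes 1.65.

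**Replaced friends.** The protocol states no rank for a friend named only once. Assume one fixed rank c for such friends and two lists of equal length n. If k friends are replaced, the ranks total n(n+1)/2 + kc at each time point, and the difference is again 0. With c = 11, replacing all 10 friends gives a numerator of 0 as written. Per-peer absolute values give 2 × (10+9+…+1) = 110.

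**Where the index as written is not zero.**

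- If only friends on both lists are counted, dropping the closest of 10 moves the other nine up one place each. The sum is −9 and the numerator is 9, the same as with per-peer absolute values.
- Tied ranks can also break the zero: 1, 2, 3 becoming 1, 1, 3 gives a numerator of 1. The protocol does not mention ties.
- Lists of unequal length can give a non-zero value too.

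**The case against.** The strongest reply is that the sentence is loose prose for summing absolute changes. The literal order of operations defeats the index's own name, and the cited source is not available here to settle what was meant. That is a fair account of intent, and the intended scoring may well be sound. It does not change what is written: the sentence fixes an order of operations, and nothing else in the document overrides it.

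The second reply is that little depends on the index. This stands. A reader might infer that results on abstinence or on differences between arms would be distorted. The documents do not support that. No aim or hypothesis in section II involves peer networks. The imputation and efficacy models use sex, school environment and dependence severity; the Hypothesis 2.1 model adds only time trends and the baseline value of the outcome. The sensitivity analyses do not use the index either.

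A reader might also infer that every participant would score 0. That is not shown. The result needs strict ranks and either identical lists or the fixed-rank coding with equal lengths. The documents do not say how often free-recall lists taken about 12 weeks apart would match.

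Finally, no particular denominator or rank for absent friends is required by the documents. Any specific choice is one workable option.

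**Conclusion.** The scoring rule is wrong as written for the construct it names. With strict ranks and the same friends at both time points, it gives 0 to every re-ordering and cannot tell a reversed list from an unchanged one. Under the further assumptions of one fixed rank for absent friends and equal list lengths, it gives 0 to turnover as well. The lost signal for a 10-friend reversal is 5.0 with one list in the denominator, or 2.5 with both.

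The severity is minor. The index is a descriptive or possible effect-modifier variable with no stated analysis. The named friends and their ranks are collected, so nothing is lost and the index can be rescored at any time.

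**What to change.** In the Peer Network Stability entry:

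1. Define the numerator as the sum, over peers, of the absolute value of each peer's rank change.
2. State whether the denominator counts one list, both lists or the distinct peers across the two time points.
3. Pre-specify how a friend named at only one time point is ranked. One option is the rank just below the last listed friend at the time point where that friend is missing.
4. Check items 2 and 3 against the cited source, so that the index stays comparable with it.

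The cost is a sentence or two of scoring text, with no new data, visits or participant burden. It is best done before the index is calculated.
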